# **Research Proposal**

## **Title: Hydrocortisone, Vitamin C, and Thiamine for the Treatment of Sepsis Associated with Acute Necrotizing Soft Tissue Infections, The NASTI HAT Trial**

**INVESTIGATORS:** [name]., [name], Pharm D., [name], M.S.N., R.N., [name], FACS, [name], FACS, [name]., [name], M.A., [name]. (Principal Investigator)

**SETTING:** Ascension Via Christi Hospital – St. Francis Campus, Wichita, Kansas

**DESIGN:** Single center, prospective, randomized, placebo controlled double-blind trial

**SAMPLE SIZE:** Will be 132 participants (66 participants per study group)

**INCLUSIONS:** All adult patients diagnosed with a necrotizing soft tissue infection and sepsis

### **I. BACKGROUND AND PRELIMINARY STUDIES:**

Necrotizing soft tissue infections (NSTIs) are a surgical emergency often presenting with concomitant sepsis. While the mortality associated with NSTIs has improved over time, it remains high at approximately 20%. Furthermore, while early surgical excision remains the mainstay of treatment and improves survival, sepsis can still lead to organ failure and death.

In 2017, [name] published a retrospective before-after clinical study proposing early use of intravenous hydrocortisone, vitamin C (ascorbic acid), and thiamine (hereafter referred to as HAT) in critically ill patients with sepsis to prevent the progression of shock to multi-system organ dysfunction, and ultimately death. A significant decrease in mortality (8.5% vs 40%) in the treatment versus control group was reported, in addition to a significant decrease in the Sepsis-Related Organ Failure Assessment (SOFA) score, and all patients in the treatment group were able to be weaned off vasopressors. Multiple rigorous randomized controlled trials have since followed and have not been able to replicate these beneficial findings. Despite this, HAT appears to be safe. Furthermore, while these and other studies have looked at varying intensive care unit (ICU) populations, to our knowledge, none have focused specifically on NSTIs. Since HAT is felt to be a safe regimen and shock is common in this population, it is reasonable to explore the use of HAT among patients with NSTIs.

### **II. STUDY OBJECTIVE:**

Evaluate the impact of HAT therapy versus placebo in the treatment of patients with an acute NSTI and sepsis.

Primary outcome:

1. Hospital survival (including those who die within 24 hours of hospital admission)

Secondary outcomes:

1. Duration of vasopressor therapy
2. Requirement for renal replacement therapy in patients with Acute Kidney Injury (AKI)
3. ICU length of stay (LOS)
4. Change in serum procalcitonin (PCT) over first 72 hours
5. Change in SOFA score over first 72 hours (measured as SOFA score daily for four days, with day one being admission, then 3 days after, totaling 4 days of treatment with HAT)
6. Procalcitonin clearance (formula = initial PCT – 72 hour PCT divided by initial PCT x 100)
7. Number of wound related surgeries
8. Wound status at time of hospital discharge:
  - a. Open
  - b. Closed

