Patients will be enrolled within 24 hours of diagnosis of sepsis related to a NSTI. HAT will be initiated within 4 hours of enrollment (thus treatment with HAT can occur no later than 28 hours from diagnosis).

Per [name] original study, HAT consists of:

- 1) 1.5 g vitamin C every 6 hours for 4 days or until ICU discharge
- 2) 50 mg hydrocortisone every 6 hours for 7 days or until ICU discharge (followed by a taper over 3 days)
- 3) 200 mg thiamine every 12 hours for 4 days or until ICU discharge

In our study, due to the prolonged ICU course typical of most patients with NSTIs, it is not felt feasible to continue indefinitely "until ICU discharge." Thus, treatment will be continued for 4 to 7 days plus a 3 day taper (respectively) as above, with no plan for a longer duration of treatment.

The control arm will receive the same standard ICU care for NSTI but will not receive HAT. They will receive a placebo consisting of normal saline, indistinguishable to the treatment team (blinded) but known to the pharmacy team (unblinded to treatment and placebo groups). This is so that if the treatment team elects to give stress dose steroids, they can be administered without breaking protocol (i.e. if the patient is getting HAT, it includes steroids, so if the treating team wanted to start hydrocortisone - because they didn't know if the patient was on HAT or placebo and felt steroids were indicated - the pharmacist could ensure the patient was on steroids one way or another without unblinding the providers).

Duration of Study:

The study enrollment period will continue for one year after its initiation, or until enrollment goal is met. Patients will be followed until hospital discharge.

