**Data Collection:**

Data will be recorded prospectively by IRB approved study personnel and entered into a shared spreadsheet on the Ascension Google Drive. See the attached spreadsheet for the specific data to be collected.

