**Variables collected will include:**

- Patient name
- Medical record number (FIN)
- Date of birth
- Date and time of diagnosis of NSTI
- Date and time of randomization
- Time from diagnosis of NSTI and sepsis to initiation of HAT: hours.
- Time on pressors prior to initiation of HAT: hours
- Patient demographics (age, gender)
- Location of NSTI infection
  - Perineum
  - Genitalia
  - Groin
  - Lower extremity
  - Upper extremity
  - Hand
  - Foot
  - Head/Neck
  - Back
  - Chest
  - Abdomen
  - Multiple/Other – free text
- Preexisting conditions – similar to [name] study:
  - None
  - Diabetes mellitus
  - Hypertension
  - Heart failure
  - Malignancy
  - Chronic obstructive pulmonary disease
  - Cirrhosis
  - Cerebrovascular accident
  - Acute Kidney Injury (AKI)
  - Chronic kidney disease
  - Morbid obesity (weight and height)
  - Immunocompromised (HIV infection, neutropenia, post-transplantation, other)
  - Active medical systemic steroid use at baseline
  - Illicit drug use evident by patient history or drug screen
  - Active tobacco or nicotine product use
- Time from diagnosis of NSTI to surgery: hours

- Total number of visits to the operating room for NSTI-related surgical intervention
- Identification of NSTI derived from pressure-related injury
- Wound status at time of ICU discharge:
  - Open
  - Closed
- Duration of vasopressor therapy: hours cumulative from entire hospitalization
- Positive blood cultures (Y/N)
- Organism present on wound culture
- Time to antibiotic use
- Antibiotic used
- Requirement for renal replacement therapy in patients with AKI (Y/N)
- Procalcitonin level daily for 4 days (with day one being admission/enrollment, then 3 days after, totaling 4 days of treatment with HAT)
- Daily SOFA score for 4 days (with day one being admission/enrollment, then 3 days after, totaling 4 days of treatment with HAT)
- Total ventilator days
- ICU LOS: Days
- Hospital length of stay: Days
- Discharge disposition: alive or deceased
- If the patient withdrew: Y/N
- Reason for patient withdrawal: Free text

Population:

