All adult patients presenting to Ascension Via Christi Hospital St Francis will be screened for inclusion and exclusion criteria. Once a potential study participant has been identified, a member of the study team will approach the patient or the patient's legal representative regarding inclusion into this study, and consent will be obtained. The length of the enrollment period of this study will be one year from the start of the study, or until the enrollment goal is met. Participants will be followed until hospital discharge.

Patient Enrollment and Random Assignment:

Patients who are admitted or diagnosed with sepsis secondary to an acute necrotizing soft tissue infection will be provided with the "Patient Informed Consent/HIPAA Authorization" document and will have the study explained to them during their initial evaluation by a member of the study team prior to enrollment. All qualifying patients who choose to participate in the study will sign the consent form, or have it signed by their legal representative. One copy of the consent form will be stored in the patient's chart and a second copy with the Research Scientist in the study files. A third copy of the consent will be provided to the patient for their reference. Randomization will be done via block randomization by the pharmacy department after a patient has consented to participate in the study.

The patient and/or his legal representative will have ample opportunity to decide whether they want to be included in this study and ask questions. The patient will be approached by a member of the study team prior to enrollment. This encounter will be within 24 hours of diagnosis, to provide ample time for consideration and to ask questions. Once consent is obtained, the HAT therapy should be started within 4 hours, such that the maximum possible time to initiation from diagnosis is 28 hours. If the patient meets inclusion criteria, then HAT or placebo (saline) will

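### Secondary outcomes 4 to 6 have no single time zero; if SOFA day one is admission, as section II says, the 72-hour window can include untreated, pre-randomisation time

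*Combined protocol and SAP*

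**What the plan says.** Section II lists eight secondary outcomes. Outcome 4 is the change in PCT over the first 72 hours, with no start given. Outcome 5 is the change in SOFA over the same period, "measured as SOFA score daily for four days, with day one being admission, then 3 days after, totaling 4 days of treatment with HAT". Outcome 6 is PCT clearance, "initial PCT – 72 hour PCT divided by initial PCT x 100", again with no start given in that section.

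The list of variables in section III words the anchor differently. For SOFA it reads "Daily SOFA score for 4 days (with day one being admission/enrollment, then 3 days after, totaling 4 days of treatment with HAT", and for PCT "Procalcitonin level daily for 4 days (with day one being admission/enrollment".

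On timing, Duration of Treatment allows enrolment up to 24 hours after diagnosis of NSTI-related sepsis and first dose up to 4 hours after enrolment, "thus treatment with HAT can occur no later than 28 hours from diagnosis". Patient Enrollment and Random Assignment repeats the limit: "such that the maximum possible time to initiation from diagnosis is 28 hours". That section covers patients either admitted with or diagnosed with the condition, and nothing limits the time from admission to diagnosis.

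Evaluations During Treatment gives a third origin. The evaluation period opens with the first administration of HAT or placebo and closes at hospital discharge, and data are collected as set out under Data Collection. That heading in turn says "See the attached spreadsheet for the specific data to be collected"; the spreadsheet is not part of the documents.

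**The concern.** A change score needs a stated baseline and a stated end. Here three events could serve as day one: admission, enrolment and first dose. On the day-one wording of section II, a patient admitted one day and first dosed the next has SOFA change counted as outcome before randomisation and before any study drug. The same happens to PCT if admission is picked from the two options in the variables list.

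The same sentence says the four days are four days of HAT treatment. For a patient first dosed on a later day, both halves of that sentence cannot be true. Staff would have to choose, and could choose differently from patient to patient.

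Three of the eight secondary outcomes depend on the choice. PCT clearance is the most exposed, because the initial value enters both numerator and denominator. Surgery is urgent or emergent, so an admission value may precede source control while a pre-dose value follows it. Inconsistent baselines would then mix surgical response with drug response.

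**Working it through.** **Inputs.** Window 72 h, with four daily scores (section II, outcomes 4 to 6). Diagnosis to enrolment at most 24 h, and enrolment to first dose at most 4 h (Duration of Treatment).

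**The plan's own figure.** 24 + 4 = 28 h from diagnosis to first dose, as stated.

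**Treated hours by anchor.** Treated hours = 72 − delay from anchor to first dose; untreated share = delay / 72.

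| Anchor and delay | Treated hours | Untreated share |
|---|---|---|
| First dose, 0 h | 72 | 0% |
| Enrolment, at most 4 h | 68 | 4/72 = 5.6% |
| Admission, 12 h | 60 | 12/72 = 16.7% |
| Admission, 24 h | 48 | 24/72 = 33.3% |
| Admission, 28 h | 44 | 28/72 = 38.9% |
| Admission, 48 h (assumed) | 24 | 48/72 = 66.7% |

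The 28 h limit runs from diagnosis, so 28 h is the maximum under the admission anchor only if diagnosis is made at admission. The 48 h row is an assumed case of later diagnosis; the documents set no upper limit there.

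**Daily scores on treatment days, admission anchor.** Let h be the clock hour of admission and d the delay to first dose. Calendar day of first dose = 1 + floor((h + d)/24). Scores on or after that day = 5 − that day.

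- d = 0: day 1, so 4 scores.
- d = 4: day 1 (4 scores) if h < 20, otherwise day 2 (3 scores).
- d = 24: always day 2, so 3 scores.
- d = 28: day 2 (3 scores) if h < 20, otherwise day 3 (2 scores).

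The stated four treatment days therefore hold only when first dose falls on the admission day.

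**PCT clearance, illustration with assumed values.** Take PCT 20 at admission, 40 just before first dose, and 10 at 72 h whichever origin is used. From admission, clearance is (20 − 10)/20 × 100 = 50%. From the pre-dose value it is (40 − 10)/40 × 100 = 75%. The figures are invented and show only that the choice of baseline can move the result.

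**What cannot be computed.** The documents give no distribution of delays and no expected effect or spread for SOFA or PCT.

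**The case against.** The strongest reply is that the intended origin can be inferred. Both statements of the SOFA schedule equate the four days with four days of treatment, which matches the four-day vitamin C and thiamine course, and Evaluations During Treatment starts evaluation at first dose. Read together, these favour a treatment-based day one. NSTI is described as a surgical emergency and the study is explained at initial evaluation, so admission, enrolment and first dose may often share a day, with little or no mismatch. The missing spreadsheet may also fix sampling times.

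Much of this stands. It limits how often the problem arises and shows what was probably meant. It does not remove the conflict: section II names admission, and the evaluation paragraph mentions neither SOFA, PCT nor baseline, so it adds a third origin without overriding the first.

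Two stronger readings are tempting and should be resisted. A reader of section II alone might infer that the initial PCT has no anchor at all. The variables list gives PCT the same ambiguous anchor as SOFA, so the fault is ambiguity. A reader might also take the untreated, pre-randomisation time as certain for every later-dosed patient. It follows only from the admission reading; from enrolment, at most 4 h are untreated and none of them precede enrolment.

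**Conclusion.** The point holds as an inconsistency with a conditional consequence. Outcomes 4 to 6 lack a single time zero. Under the admission anchor, up to 28 of 72 h are untreated if diagnosis is made at admission, and more if it comes later. Under the enrolment anchor the most is 4 h.

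A reader might infer bias between the arms. The documents do not support that: any delay before enrolment precedes randomisation, the treating team is blinded, and the arms should be affected alike. The expected effect is to dilute the contrast and add noise, by an amount that varies between patients. Hospital survival and the sample size of 132 are unaffected. A loss of power for these outcomes is plausible but cannot be quantified. Severity is minor.

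**What to change.** In section II and in the variables list, delete admission as day one and use randomisation as time zero for outcomes 4, 5 and 6. Its date and time are already collected, it exists for every randomised patient, and it follows consent, so it is at most about 4 h before first dose. Define baseline SOFA and initial PCT as the last value before the first dose of HAT or placebo or, for a patient never dosed, the value nearest randomisation. Take the final value 72 h after randomisation, within a stated sampling window.

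Randomisation is preferable to first dose as the origin because a patient randomised but never dosed would otherwise have no time zero. The existing item "Time from diagnosis of NSTI and sepsis to initiation of HAT: hours" should be worded to cover placebo as well, so that the last pre-dose value can be identified in both arms.

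The cost is wording in two places. For patients enrolled after the day of admission, the SOFA and PCT assessments are re-timed. The primary outcome and sample size do not change.

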**VI. STATISTICAL ANALYSIS:**

The data that is collected will be compiled, evaluated and summarized by calculating means and standard deviations for continuous data, medians and quartiles for ordinal data, and proportions for discrete data. One-way analysis of variance will be utilized to compare continuous data. Where heterogeneity of variance is identified, data will be either transformed and analyses rerun, or data will be analyzed using the Mann-Whitney U-Test. Chi-square analysis will be utilized for comparison of categorical data. Ordinal data will be analyzed using the Mann Whitney U-Test. Logistic regression analyses will be utilized to identify independent predictors of the outcomes variables of interest. All analyses will be run as two-tailed tests and results of analyses will be considered significant if the resultant P-value is less than or equal to 0.05. Analyses will be run using SPSS 19.0.

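### Procalcitonin outcomes: the clearance formula fails as written, the change outcome is undefined, and the default ANOVA on unlogged, unadjusted values loses power

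*Combined protocol and SAP*

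**What the plan says.** Section II (Study Objective) lists two procalcitonin outcomes among its eight secondary outcomes. Outcome 4 is "Change in serum procalcitonin (PCT) over first 72 hours", with no formula. Outcome 6 is "Procalcitonin clearance (formula = initial PCT – 72 hour PCT divided by initial PCT x 100", with no brackets around the subtraction. The neighbouring SOFA change outcome does name its measurements: "measured as SOFA score daily for four days, with day one being admission, then 3 days after, totaling 4 days of treatment with HAT".

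The list of variables in Section III collects "Procalcitonin level daily for 4 days (with day one being admission/enrollment, then 3 days after, totaling 4 days of treatment with HAT", so four PCT values per patient should exist.

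Section VI (Statistical Analysis) summarises by "calculating means and standard deviations for continuous data" and states that "One-way analysis of variance will be utilized to compare continuous data". Only where variances are found to differ does it say that "data will be either transformed and analyses rerun, or data will be analyzed using the Mann-Whitney U-Test". Every test is judged alike: "results of analyses will be considered significant if the resultant P-value is less than or equal to 0.05". The section names no baseline covariate for continuous outcomes, no adjustment for multiple tests, and no rule for a missing 72-hour value.

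**The concern.** There are three separate problems.

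- **Formula.** The formula in outcome 6 does not return clearance if it is typed as written, and the data are to be kept in a spreadsheet.
- **Definition.** Outcome 4 could be a raw difference, a relative change or a trajectory over four days. Under the raw-difference reading, the trial tests one question twice on the same two numbers, each at 0.05 and with no stated priority.
- **Method.** For a right-skewed marker, means and ANOVA on unlogged values are inefficient, and the initial PCT that is already collected goes unused. The fallback is triggered by unequal variances, not by skew.

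At stake is whether the trial can read a PCT effect if one exists, and whether that reading depends on choices made after the data are seen.

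**Working it through.** **1. The plan's own figure.** The plan gives no figure for either PCT outcome. Its one design figure is 66 per group for mortality of 20% against 4.24% (Section VII). With mean proportion 0.1212, two-sided α 0.05 and power 80%:

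n = [1.96·√(2 × 0.1212 × 0.8788) + 0.8416·√(0.20 × 0.80 + 0.0424 × 0.9576)]² / 0.1576² = (0.9046 + 0.3770)² / 0.02484 ≈ 66.1

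This is 67 when rounded up, and power at 66 is 79.9%. The figure reproduces to within one patient, and nothing below changes it.

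**2. The clearance formula.** Let I be initial PCT and F be 72-hour PCT. As written, in normal operator order, the score is I − 100·F/I. The intended clearance is 100·(I − F)/I = 100 − 100·F/I. The written version is therefore off by I − 100, which depends on the initial value.

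| I → F | As written | Intended |
|---|---|---|
| 20 → 5 | −5 | 75% |
| 2 → 0.5 | −23 | 75% |
| 20 → 20 | −80 | 0% |
| 2 → 2 | −98 | 0% |
| 100 → 25 | 75 | 75% (agrees only because I = 100) |

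**3. Outcome 4, if it is I − F.** Falls of 100 to 25, 20 to 5 and 2 to 0.5 are all 75% clearance, but the raw changes are 75, 15 and 1.5. How far raw change tracks initial PCT depends on variability that the documents do not give. I assumed log-normal values, with SD of log I 0.5–2.0, SD of log(F/I) 0.3–1.2 and median F/I 0.25–0.60. The rank correlation of raw change with I then runs from 0.25 to 1.00 (squared, 0.06 to 1.00). At SD of log I 1.0 and SD of log(F/I) 0.8, the squared value is 0.71, 0.41 and 0.16 for median ratios of 0.25, 0.40 and 0.60.

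**4. Power by method (simulation; all PCT inputs assumed).** 66 per arm, all with both values. Initial log PCT is normal around log 15 with SD 0.7, 1.0, 1.3 or 1.6. 72-hour log PCT = log 15 + log 0.3 + 0.8 × (initial log PCT − log 15) + log 0.7 on HAT + normal error with SD 0.6 or 0.9.

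| Analysis | Power |
|---|---|
| Raw change, ANOVA | 4–16% |
| Raw change, Mann-Whitney | 9–21% |
| Clearance, ANOVA | 41–85% |
| Clearance, Mann-Whitney | 53–89% |
| Log ratio, unadjusted | 55–91% |
| Log 72-hour PCT adjusted for log initial PCT | 61–92% |

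Hand check of the last row: the effect is log 0.7 = −0.357 and the standard error is 0.6·√(2/66) = 0.104 or 0.9·√(2/66) = 0.157. This gives z = 3.42 or 2.28, and power Φ(z − 1.96) of about 93% or 62%.

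**5. A second set of assumptions.** Here the median ratio is 0.40, HAT multiplies it by 0.67, SD of log ratio is 0.8, SD of log initial PCT is 0.8–1.5, and the ratio is independent of initial PCT. Power is 8–27% for raw change by ANOVA, 68–70% for clearance by ANOVA, 78–80% for clearance by Mann-Whitney, and 81–83% for the adjusted log model. With SD of log ratio 1.2 and SD of log initial PCT 1.2, these become 12%, 29%, 46% and 48%. The ordering is the same.

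**6. How the scales relate.** Clearance = 100 × (1 − exp(log ratio)), a one-to-one function, so Mann-Whitney gives the same p-value for both. With log initial PCT as covariate, regressing log F or log(F/I) gives the same arm coefficient, because subtracting the covariate changes only its own slope.

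**The case against.** The strongest reply is that much of this is choice of method, and that the certain error is a typing slip. The word clearance and the order of terms make the intent plain, and brackets alone repair outcome 6. That stands.

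Several stronger readings are tempting, and the documents do not support them:

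- **That outcome 4 is a raw difference of the same two values as outcome 6.** Section II does not say so. Four daily values are collected and the parallel SOFA outcome is framed by daily scores, so a trajectory is a fair reading. What can be said is that outcome 4 is undefined.
- **That raw change mostly reflects initial PCT.** This holds when initial PCT varies widely and the fall is large and fairly uniform. It fails when clearance varies a lot or the typical fall is small (step 3).
- **That the percent scale is itself the fault.** Clearance by Mann-Whitney comes within a few points of the unadjusted log ratio. Most of the deficit comes from ANOVA on a skewed quantity. Section VI does name Mann-Whitney, but only as one of two options and only for unequal variances, so it is not assured.
- **That one patient can wreck the mean.** A rise from 0.5 to 20 scores −3900% and shifts a 66-patient mean by 3900/66 ≈ 59 points. Under the model in step 4, however, a 40-fold rise has a probability of at most about 1.5 in 10 million per control patient.
- **That the planned transformation cannot be done because differences can be negative.** Section VI does not name the transformation, and nothing prevents logging PCT before differencing.

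**Conclusion.** The point holds in a limited form. It is certain that the outcome 6 formula, evaluated as written, does not give clearance, and that outcome 4 lacks a scale and time points. It is conditional that, if outcome 4 is the raw difference, it duplicates outcome 6's inputs and has low power: about 4–16% by ANOVA under the assumptions in step 4. On method, the default ANOVA is less efficient than a log-scale model that uses the initial value, with 41–85% for clearance against 61–92%. Against clearance by Mann-Whitney (53–89%) the gain is small.

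All the power figures rest on an assumed PCT distribution and effect, and on complete data in 66 per arm. A reader might infer that the PCT result would be uninterpretable. That goes too far, since bracketed clearance can be interpreted. These are two of eight secondary outcomes, and the primary outcome and the 132 participants are untouched. The change is worth making because it is nearly free.

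**What to change.** In Section II, write clearance as 100 × (initial PCT − 72-hour PCT) / initial PCT. Replace the two tested PCT outcomes with one prespecified comparison: log 72-hour PCT (equivalently the log ratio) regressed on arm and log initial PCT, reported as a ratio of geometric means with its confidence interval. Report clearance descriptively, not as a second test. Add one line to Section VI naming this model. If a trajectory over the four daily values was meant for outcome 4, the plan should say so instead of leaving it open.

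The cost is a wording change in Section II and a line in Section VI, with no new data. Values below the assay limit need a stated substitute. The model does not settle which sample counts as initial (the variable list allows admission or enrollment), nor how deaths or withdrawals before 72 hours are handled. Both need their own sentence.

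### The single count of wound-related operations pools debridement with closure surgery, so a difference between arms has no clear direction

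*Combined protocol and SAP*

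**What the plan says.** Section II lists "Number of wound related surgeries" as secondary outcome 7, with no definition, time window or direction of benefit. In Section III, the list of variables gives the matching field as "Total number of visits to the operating room for NSTI-related surgical intervention". No listed field separates debridement, amputation and closure or grafting, although the infection sites include upper and lower extremity, hand and foot.

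Closure is an outcome in its own right. Outcome 8 is "Wound status at time of hospital discharge", open or closed. The variables list instead has "Wound status at time of ICU discharge", so the two sections disagree on the time point.

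The Duration of Study paragraph says "Patients will be followed until hospital discharge", so death in hospital ends the count. Section VI has nothing specific to this outcome: "One-way analysis of variance will be utilized to compare continuous data", with transformation or the Mann-Whitney test if variances differ. "All analyses will be run as two-tailed tests", and a result is "considered significant if the resultant P-value is less than or equal to 0.05".

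**The concern.** A patient may return to the operating room because infection is not controlled, or because the wound is ready to be closed. The first is what an effective sepsis treatment might reduce; the second is what it might make more common. A patient closed in the operating room adds to outcome 7 through the very event that outcome 8 records as closed.

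Three things follow. A higher count on HAT could mean more infection or more recovery. A true fall in debridements could be diluted by extra closures. If HAT improves survival, more patients live long enough to be closed, which pushes the total up. An early amputation that is then closed would also look the same in the listed data as a limb-preserving recovery: few operations and a closed wound.

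**Working it through.** **The plan's own figure.** The plan gives no figure for this outcome. Its sample size supplies the number per arm and the mortality rates used below, so it was checked first. With p1 = 0.20, p2 = 0.0424, mean 0.1212, two-sided 0.05 and 80% power, pooled variance:

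n = [1.96·√(2·0.1212·0.8788) + 0.8416·√(0.20·0.80 + 0.0424·0.9576)]² / 0.1576² = (0.905 + 0.377)² / 0.02484 ≈ 66.1.

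This is 67 rounded up, against 66 stated. Power at 66 is 79.9%. The figure reproduces, and the present point does not depend on it.

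**Assumed inputs (not in the documents).** Debridements average 2.0 per control patient. They are Poisson, or overdispersed (negative binomial, shape 1, variance m + m²). Each closed survivor has 1 + Poisson(0.5) closure operations, mean 1.5; a variant uses exactly one. The count is tested as continuous data.

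**Formulas.** Let q = P(alive) × P(closed if alive).
- Mean total = debridements + 1.5q.
- Closure variance = 2.75q − (1.5q)², or q(1 − q) with one operation per closure.
- Chance of a significant result ≈ Φ(|d|/SE − 1.96) + Φ(−|d|/SE − 1.96), with SE = √[(V_control + V_HAT)/66].

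**Worked example: debridements 2.0 to 1.4, closure 50% to 65%, 20% mortality in both arms.**
- Debridements: d = −0.60, SE = √[(2.0 + 1.4)/66] = 0.227, ratio 2.64, power 75%.
- Total, control: q = 0.40, mean 2.60, variance 2.0 + 0.74 = 2.74.
- Total, HAT: q = 0.52, mean 2.18, variance 1.4 + 0.82 = 2.22.
- d = −0.42, SE = √(4.96/66) = 0.274, ratio 1.53, power 33%.

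**All scenarios** (chance of a significant result; 5% is expected with no difference):

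| Scenario | HAT minus control | Poisson | Overdispersed |
|---|---|---|---|
| Debridements 2.0 to 1.4, debridements only | −0.60 | 75% | 36% |
| Same, closure 50% to 65%, total, equal mortality | −0.42 | 33% | 18% |
| Same, total, 20% vs 4.24% mortality | −0.27 | 16% | 10% |
| Debridements unchanged, closure 50% to 70%, total, equal mortality | +0.24 | 13% | 8% |
| Same, one operation per closure | +0.16 | 9% | 7% |
| Debridements unchanged, closure 50% to 70%, total, 20% vs 4.24% mortality | +0.41 | 29% | 15% |
| Same, one operation per closure | +0.27 | 18% | 10% |

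Simulation agrees to within about two percentage points; for example, 13 to 14% in the fourth row, and 35 to 37% and 17% for the overdispersed figures in the first two. Under Poisson counts the Mann-Whitney fallback gave 30%, 14% and 28% for the total in the second, third and sixth rows, so the problem is not specific to ANOVA.

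**The sign is not fixed.** Take 3 debridements per control patient, one operation per closure, closure 50% to 70%, and no deaths. The difference is +0.2 if debridements stay at 3, 0 if they fall to 2.8, and −0.8 if they fall to 2.0.

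**Death shortens any count.** The table draws debridements independently of death. If survivors have 4 operations and those who die have 1 to 2, in both arms, the plan's mortality alone makes the HAT mean higher by (4 − 2) × 0.1576 = 0.32 to (4 − 1) × 0.1576 = 0.47. A debridement count is exposed to the same effect.

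**The case against.** Four objections have force.

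- **Direction.** A reader might infer that the plan scores a patient who reaches closure as worse, or an early amputation as the best result. The documents do not support this. They assign no direction to outcome 7, all tests are two-tailed, and no ranking, composite or decision uses the count. The fault is ambiguity.
- **What is counted and recorded.** The text never says that closures count; that is the ordinary reading of the wording. Section III also refers to an attached spreadsheet that is not among the documents, and the variables list need not be exhaustive. A procedure-type or amputation column may exist there.
- **Outcome 8 already reports closure.** This helps: fewer operations with equal or better closure is readable, leaving deaths aside. But open or closed does not show how many visits were closures. More operations with more closure, or equal counts with more closure, stay unclear. The differing time points for wound status weaken the cross-reading further.
- **Total operations is a legitimate measure of surgical burden.** This stands, and is a reason to keep the total beside a typed count.

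A reader might also infer that better closure alone would often produce a significant excess of surgery on HAT. The figures do not support that: at equal mortality it is 9 to 14% with Poisson counts and 7 to 8% with overdispersion, against 5% by chance. The larger figures need the plan's mortality difference as well.

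**Conclusion.** The point holds as a fault of interpretation in one secondary outcome. As listed, the count can rise through worse infection or through recovery, and the listed variables cannot show which.

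The more substantial effect in the illustrations is dilution: power for a real fall in debridements drops from about 75% to 33%, or from about 36% to 18% with overdispersion, and lower still if HAT reduces mortality as the plan assumes. A significant excess from closure alone is possible but uncommon; with the plan's mortality difference and 1.5 operations per closure it reaches about 15 to 29%.

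Every surgical input is an assumption, and the results move with dispersion, operations per closure and mortality. The conclusion also rests on the ordinary reading of the outcome and on the listed variables being those collected. The primary outcome and the sample size are unaffected.

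**What to change.** 1. For each operating-room visit after randomisation, record the date and type from the operative note: debridement, amputation, or closure/graft/flap. If the attached spreadsheet already has these fields, cite them in the outcome definition.
2. Analyse the number of debridements after randomisation as the infection-control measure for outcome 7, and state that fewer is better.
3. Keep the total number of visits as a descriptive measure of surgical burden.
4. Report closure operations and amputation (yes/no) by arm beside outcome 8, and reconcile its time point between Sections II and III.
5. State in advance how deaths before discharge are handled; for example, also report debridements among survivors and per day alive in hospital. The survivor figure is descriptive, because survival may itself differ by arm.

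The cost is about three spreadsheet columns, a few lines in the outcome definition, and a coding rule for a visit that combines debridement and closure (count it as a debridement). Patient care, sample size and the primary analysis do not change. If type is not recorded during the trial, recovering it later means re-abstracting every chart.
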